## Appendix I – Recruitment Script

The script that would be provided to clinicians would be as follows:

“There is a research project that is running at CAMH that you might be interested in. It focuses on studying a cognitive intervention that is designed to help people who have experienced psychosis have more success in reaching their goals for recovery. The intervention uses a number of cognitive strategies, and if you took part you would receive personalized environmental supports for your space on the unit. If you are interested, I’d put you **[add if required: and your substitute decision maker]** in touch with the researchers who would tell you more about it. It is completely fine to say no and take a pass on this. Saying no won’t affect the care you receive here at any time, now or in the future. Feel free to take some time to think about it as well. What do you think?”

**Appendix II – CAT Referral Form**

Cognitive Adaptation Training Referral			
Unit/Service at time of Documentation			
Referral Requested By			
Primary Nurse or Case Manager			
Date of Referral			
Who should be contacted for information or questions regarding this referral?			
Name			
Extension			
Current Psychiatric Status			
 At baseline	 Persistent negative symptoms	 Active substance use	
 Actively psychotic	 Persistent positive symptoms		
 Has insight into symptoms	 No persistent symptoms		
Housing Type			
 Inpatient	 With Family/Spouse	 Boarding Home	
 Independent	 Homeless/Shelter	 Meals Provided	
 Supported	 Transitional	 Housing at Risk	
Approx. Length of Time in Current Housing			
Approx. Time to Discharge or Transfer		 1-2 months	 3-6 months
		 6 months +	
– NOTE TO OUTPATIENT CLINICIANS – PLEASE COMPLETE PRE-VISIT HOME SAFETY RISK ASSESSMENT POWERFORM			
Client Factors			
 Paranoia	 Engaged with Staff	 Independent in ADLS	 Involved in Work
 Insight into Illness	 Engaged with Family	 Hoarding	 Involved in School
 Antisocial PD	 Social Involvement	 Infestations/Bedbugs	 Involved in Volunteering
Clinical Goals			
 CAT Clean Rooms	 Personal Hygiene	 Social Skills	 Diet/Weight Management
 Home Safety	 Dental Hygiene	 Stress Management	 Employment Connection
 Attendance	 Housing Keeping	 Budgeting	 Education Connection
 Medication Management	 Organization	 Cooking	 Leisure Connection
 Transportation	 Harm Reduction		
Other relevant details or goal areas:			
Is client agreeable to referral?		 Yes  No	
Has client participated in CAT before?		 Yes  No	
Reasons for Re-Referral			
Complete FORCAT Referral Order		 Yes	

## Appendix III – Focus Group Script

“Welcome to the focus group for the fin-CAT study. The purpose of this focus group is to gather feedback on the recent introduction of finCAT to your unit. Specifically, we are interested in your feelings about finCAT as well as your thoughts about its impact and challenges during implementation.

Before we begin, I want to remind you about a few key pieces of information:

- All the information you provide during the focus group will be kept both confidential and anonymous
- You do not need to answer any question you are uncomfortable answering
- You may withdraw from the focus group at any time without reason
- You will not be compensated for your time in the study
- From your previous individual consents, we will record this session for research purposes. If have changed your mind and no longer wish to be recorded, please inform the researcher and you will be offered alternative accommodations.

The facilitator has 7 questions to prompt discussion. We value honest input and will use your feedback to improve the finCAT program moving forward. We would like to review the following ground rules before we get started:

- Don't hold back. It is safe for you to freely express your opinions without consequence. We also ask that you respect confidentiality of the information discussed in today's group.
- Please try to avoid sidebars (separate conversations, or body-language sidebars like eye-rolling, etc.).

Please set your phones to vibrate or off. You have right to challenge, criticize and/or disagree during the decision/discussion. All opinions are valued in this setting.

Does anyone have any questions before we get started?

Provider Focus Group Questions

1. How do you feel finCAT has influenced, if at all, your clients' organization on the unit?
  - a. If positively influenced, in what areas specifically did you see improvement?
  - b. If negatively influence, in what areas specifically did you see this?
2. How do you feel finCAT has influenced, if at all, your clients' self-care on the unit?
  - a. If positively influenced, in what areas specifically did you see improvement?
  - b. If negatively influence, in what areas specifically did you see this?
3. How did your clients respond to finCAT within your sessions?
  - a. How did that evolve throughout the course of implementing the program?
  - b. How can finCAT be further adapted to meet the needs of clients within an inpatient forensic practice setting?
4. How do you feel finCAT has influenced the relationship between clinicians on the unit?
  - a. Can you describe how finCAT contributed to any potential conflict or tension on your unit?
  - b. Did any challenges arise implementing finCAT inter-professionally?
5. How was the process of incorporating finCAT into your practice setting?
  - a. What factors supported the use of finCAT?

- b. What barriers did you come across in your practice?
- 6. What are your thoughts about the training sessions on finCAT
  - a. What did you like? What didn't you like?
  - b. What did you like about the format (e.g., length of sessions, # of attendees, facilitators)?
  - c. How could the training be improved?
  - d. Was the training for finCAT sufficient for your learning?
- 7. Any additional thoughts or comments that you would like to share?

#### Individual Interview Questions for Clients

- 1. How do you feel finCAT has influenced, if at all, your room organization on the unit?
  - a. What improvements did you notice about your room?
  - b. Do you think there is more room for improvement?
- 2. How do you feel finCAT has influenced, if at all, your self-care on the unit?
  - a. What improvements related to self-care (e.g., personal hygiene) do you feel you've had?
  - b. Do you think there is more room for improvement?
- 3. How did you feel during the finCAT sessions?
  - a. What made you feel that way?
- 4. What did you enjoy about finCAT?
- 5. What did you not enjoy about finCAT?
- 6. How did you find finCAT influenced your relationships with clinicians on the unit?
- 7. Any additional thoughts or comments that you would like to share?

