### ***Safety Protocol***

A CAT Clinician will be providing direct care to inpatient forensic clients with the support of Unit Champions who are familiar with both the client and the unit milieu. All CAT Clinicians and investigators will check in with the treatment team immediately prior to each interaction with inpatient clients and wear a personal alarm according to unit protocols. Investigators will make best efforts to meet with clients with Unit Champions. Student investigators will be accompanied by study or unit staff in all interactions. CAT interventions will in no way involve taking clients off the unit, and all investigators will exercise AWOL caution at unit entry points.

All environmental support supplies provided to clients will align with individualized unit policies and procedures, including but not limited to restrictions of no metal, no glass, no sharp objects, and no long ropes/strings. All items provided will be items participants could potentially purchase independently.

Research personnel may withdraw a participant from the study early if the researchers do not think it is in the participant's best interest to continue. Research personnel will discuss the reasons for the withdrawal with the participant. The study doctor may also end a participant's involvement in the study early, without their consent, for reasons such as:

- The study intervention does not work for them
- The participant is unable to tolerate the study intervention
- The participant is unable to complete all required study procedures

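### The client interview's follow-up probes on room organization and self-care presuppose improvement and lack the negative branch that providers are given for the same two domains

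*Combined protocol and SAP*

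**What the plan says.** The client guide (Appendix III, Individual Interview Questions for Clients) has seven main questions. Question 1 opens "How do you feel finCAT has influenced, if at all, your room organization on the unit", and question 2 has the same form for self-care. The follow-ups are "What improvements did you notice about your room" (1a) and "What improvements related to self-care (e.g., personal hygiene) do you feel you've had" (2a), each followed by "Do you think there is more room for improvement" (1b and 2b). Later questions cover how the client felt in sessions, what they liked, what they disliked, and relationships with clinicians, ending with an open invitation to comment.

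The provider guide in the same appendix uses matching stems for the same two domains. Each stem is followed by one probe that applies if the influence was positive and one that applies if it was negative: "If negatively influence, in what areas specifically did you see this".

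On the setting, the Measures section (Qualitative Care Provider & Participant Attitudes) has student investigators run the client interviews. The Safety Protocol states: "Student investigators will be accompanied by study or unit staff in all interactions". It also asks investigators to try to see clients together with a Unit Champion.

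**The concern.** A probe that asks which improvements were noticed takes for granted that there were some. A client who has just answered the stem with no change, or a change for the worse, is next asked to list benefits. Room organization and personal hygiene are the two goal areas of finCAT (Study Design Overview), so the one-sided follow-ups fall on the questions about whether clients think the intervention worked.

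The study has a single group and is meant to inform adjustments to the intervention (The Proposed Project). That use needs reports of no effect and of harm as much as reports of benefit. The planned safeguards in Data Analysis, two independent coders and team review of code summaries, act on the transcripts and cannot recover what the interview did not draw out.

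The setting raises a separate question. A forensic inpatient may find it harder to voice criticism when someone from the unit that provides their care, or someone who maintains finCAT there, is in the room.

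**Working it through.** No formula applies, and the plan gives no figure to reproduce. The check is a side-by-side reading and a count.

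**Step 1: follow-ups in the two effect domains.**

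| Feature | Client guide, questions 1 and 2 | Provider guide, questions 1 and 2 |
|---|---|---|
| Stem | Neutral, allows no effect | Neutral, allows no effect |
| Follow-up probes | 4 | 4 |
| Presuppose improvement | 2 (1a, 2a) | 0 |
| Ask about further room for improvement | 2 (1b, 2b) | 0 |
| Positive, conditional on a positive influence | 0 | 2 |
| Negative, conditional on a negative influence | 0 | 2 |

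So 2 + 2 = 4 of 4 client follow-ups are framed around improvement and 0 of 4 ask about worsening, against 2 of 4 for providers. The stems match, so the difference lies in the follow-ups alone.

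**Step 2: the rest of the client guide.** Of the 7 main questions, 5 are neutral or open (1, 2, 3, 6, 7), 1 is positive (4) and 1 is negative (5). Question 3, "How did you feel during the finCAT sessions", and its follow-up are neutral. Questions 4 and 5 form a like/dislike pair. Question 6, "How did you find finCAT influenced your relationships with clinicians on the unit", does not lean either way. The questions that bear on acceptability are therefore balanced, and the wording problem is confined to probes 1a and 2a.

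**Step 3: who may be in the room.** Student investigators conduct the interviews, and the accompaniment rule covers all their interactions, so it covers these. It is met by study staff or by unit staff, and the plan does not say which will attend client interviews. The request to see clients with Unit Champions makes a Champion's presence a real possibility. Champions are the unit's own allied health staff (CAT Fidelity) and carry the two-month maintenance phase (Study Design Overview). The Confidentiality section places assessments in a private space, but this does not exclude an accompanying staff member. Presence of unit staff is thus permitted but not certain.

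**Step 4: what is exposed.** Data Analysis names the CIRS, GAS and Life Skills Profile scores as primary. None of these comes from the interview. The CIRS is rated from photographs by two blinded raters, the Life Skills Profile self-care items by nursing staff not directly involved in delivery, and the GAS by consensus of clinician and case manager.

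**The case against.** The strongest reply is that the client guide already invites bad news. The stems allow a client to report no effect or a negative one before any probe is used, 1b and 2b can bring out shortfall, and question 5 asks outright what was disliked. This stands, and it limits the point to the follow-ups. What it does not supply is an explicit prompt about worsening, or a follow-up that suits a client who reports none of the assumed benefit.

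Several stronger readings are tempting and are not supported:

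- A reader might infer that the interview asks only about improvements. Questions 3 to 7 show otherwise.
- A reader might infer that leading wording distorts acceptability findings. Those questions are balanced, and acceptability also draws on a purpose-made feedback form (Measures) and a session-attendance profile (Data Analysis), so the interviews are not its only source.
- A reader might infer that client and provider themes cannot be compared. The stems match, so comparison remains possible; it needs caution in these two domains. Nor is the provider guide even throughout: probe 4a asks only about conflict or tension, and 6b only about what was liked in the format.
- A reader might infer that treating staff will attend. The rule is a safety provision that study staff alone can satisfy.

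It can also be said that this is follow-up wording in a 24-person feasibility study and touches no planned test. That is true and keeps the point modest. It does not argue against an edit that costs nothing.

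**Conclusion.** The point holds in a limited form. Client themes on perceived change in room organization and self-care are at risk of favourable bias, because probes 1a and 2a presuppose benefit and the balanced form used elsewhere in the same appendix was not carried over. Client acceptability themes carry no such wording risk. For them, what remains is the possible presence of unit staff or a Unit Champion.

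The documents give nothing from which to compute the size or confirm the occurrence of either bias, so both are stated as risks. The conclusion assumes that interviewers use the probes as printed and that the Safety Protocol's accompaniment rule applies to client interviews, as its wording indicates. The interviews fall at the end of each unit's schedule (Study Overview), so the guide should be corrected before they begin.

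**What to change.** Keep the neutral stems of client questions 1 and 2. Replace probes 1a and 2a with the provider structure, in words such as: *If positively influenced, in what way? If negatively influenced, in what way?* Probes 1b and 2b can stay. This is an appendix edit with no cost to the conduct of the study.

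As a secondary step, add a sentence that, within the Safety Protocol's existing choice between study and unit staff, the preferred companion for client interviews is a member of study staff who did not deliver finCAT, where unit safety rules allow. Record who was present at each interview, so that the analysts can take it into account when reading the themes. Accompaniment itself is unchanged; the cost is some scheduling effort.
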